## 8.2 Co-enrolment Guidelines

Patients who are already enrolled in observational studies will be eligible for coenrolment with the EViSCO study. Patients who have been recruited to the EViSCO study are eligible for co-enrolment in other observational studies. The Co-enrolment Form within the Case Report Form (CRF) should be completed and submitted to the CTU. Participants who have been enrolled in other IMP trials within the last 30 days will not be eligible for co-enrolment in EViSCO. Co-enrolment with other interventional studies will not be permitted.

### 8.3 Unblinding Procedure

As a placebo controlled, double-blind trial, patients, clinicians and the CI will be blinded to treatment allocation. Patients will be given a Patient Study Card when they are enrolled in the trial. This will include 24-hour contact details of their treating clinician in the event that the patient needs to contact their clinician. Emergency unblinding may be requested on safety grounds, or if the treatment decision for a patient could be influenced by the knowledge of what the patient is taking as part of the trial. If there is justification to unblind a patient, emergency unblinding will be performed by the Belfast Trust on call pharmacist. In the event unblinding occurs, the patient may discontinue study drug but will remain on the trial unless they decide to withdraw. Where unblinding has occurred this should be fully documented by the site and the Sponsor and NICTU informed.

## 9 STUDY DRUG

## 9.1 Treatment Regimen

Patients will be randomised to receive valaciclovir 1 gram to be taken 3 times daily or matching placebo for 8 weeks. Patients will continue on treatment until they attend for visit 3 (Week 8 +/- 7 days) assessment.

### 9.2 Concomitant Therapy

Patients will be allowed to continue their COPD therapy which usually consists of inhaled short acting beta agonist, inhaled antimuscarinic therapy- typically a long acting agent, an inhaled long acting bronchodilator and an inhaled steroid. Medication for other conditions will be continued provided they are not interacting with the investigational medication. If there is an interacting drug as outlined in the exclusion criteria they will not be included in the trial.

## 9.3 Study Drug Supply

Study drug packs will be packaged and labelled by Victoria Pharmaceuticals, [name]. Study drug packs consist of:

Valaciclovir 500mg capsules in bottles containing 210 capsules

Matched placebo (Avicel®PH) capsules in bottles containing 210 capsules

Study drug packs of valaciclovir 500mg or placebo capsules will be labelled in compliance with the applicable regulatory requirements. Study drug packs will be dispatched to the responsible site pharmacist under the instruction of the CI or designee. The CI or designee will monitor the quantity of study drug packs at site to ensure study drug packs are available to facilitate the supply of study drug to patients at the time of recruitment/randomisation and at subsequent study visits.

## 9.4 Study Drug Accountability

Pharmacy will maintain accurate records of all Investigational Medicinal Product (IMP) received (including date of receipt, batch numbers, expiry date, quantities of drug shipments), dispensed and returned on the Drug Accountability Log. Records must be available to the study monitors on request. Unallocated, unused and used study drug will be destroyed at site with permission from the CTU and in accordance with site pharmacy procedure for destruction of IMP and hospital waste management policies. A record of the destruction will be maintained.

## 9.5 Storage of Study Drug

Site pharmacies must ensure all study drugs are stored in a secured area and held separately from normal hospital stock and under the manufacturer's recommended storage conditions as detailed on the study drug pack label.

## 9.6 Study Drug Dispensing

When a patient is recruited at visit 1 (baseline) and subsequently at visit 2 (week 4) the clinician will complete a trial prescription form and present this to pharmacy. At visit 1 and 2 (baseline and week 4), patients will receive a four week supply (plus one week overage) of valaciclovir 500mg or placebo capsules

## 9.7 Study Drug Administration

Patients will take valaciclovir 1 gram (2 x 500mg capsules) or matching placebo capsules orally three times daily for 8 weeks .

## 9.8 Study Drug Termination Criteria

Prior to the maximum treatment period of 8 weeks (after randomisation), study drug will be discontinued if any of the following conditions are met:

- Patient request termination of study drug
- Patient withdraws consent for the study
- Non-compliance with study drug as determined by the PI
- PI decision that study drug should be discontinued on safety grounds.

The reason for study drug termination should be recorded on the CRF and arrangements will be made for any unused medication to be returned to pharmacy.

## 9.9 Study Drug Compliance

Patients will be asked to store the medication according to the manufacturer's instructions as detailed on study drug pack label. Patients will be asked to bring all unused medication and empty bottles to visit 2 and visit 3. Research staff will perform a count and return any unused medication and empty bottles to the site pharmacy. Patients who have taken 80% or more of the expected number of tablets will be considered compliant. Non-compliance should be discussed with the PI to determine the appropriateness of continuing/discontinuing the medication.

## **10 STUDY ASSESSMENTS**

## **10.1 Study Visits and Procedures**

Study visits must be accurately recorded in participants medical notes i.e. screening and baseline visits. All details to confirm eligibility should be retained in the participant's medical notes. Medical notes are source documents.

## **10.1.1 Screening Visit Procedures**

The consent process will be conducted at the screening visit. Screening blood U&E samples will be taken (if required). Medical and Medication history will be reviewed, demographic data and screening sputum samples will be obtained. Patients in whom the screening sputum sample is found to be positive for EBV (measured by quantitative PCR) will be advised and invited to return for measurement of lung function. Those patients found to be eligible will then be invited to take part in the study. Patients who suffer an exacerbation of COPD in the interim period between the screening and baseline visits will be invited to be re-screened following clinical resolution of the exacerbation. Patients in whom sputum EBV qPCR is negative may be given the opportunity to return to be re-screened at a later date.

### 10.1.2 Visit 1 (Baseline) Procedures

Medical history, medication history, vital signs and BMI will be recorded at the baseline visit. Participants will complete CAT and EQ-5D-5L assessments.. FBC, research blood and sputum samples will be taken. Participants will be asked regarding exacerbation status and if applicable exacerbations will be documented. Four weeks supply of the study drug or placebo will be given and an appointment for follow up will be made. The GP will be informed via written correspondence. Substudy volunteers will undergo diagnostic bronchoscopy.

### 10.1.3 Visit 2 (Week 4 +/- 7days) Procedures

Participants will undergo assessment via telephone call (including medication review and recording of adverse events). CAT and EQ-5D-5L assessments will be completed remotely via telephone call. Participants will be asked regarding exacerbation status and if applicable exacerbations will be documented. A sputum sample will be left for collection by the participant .Participants will count surplus medication and advise the researcher of the tablet count . A new 4-week supply of medication will be dispensed.

### 10.1.4 Visit 3 (Week 8 +/- 7 days) Procedures

Participants will undergo assessment via telephone call (medication review and recording of adverse events).. Participants will complete CAT and EQ-5D-5L assessments remotely via telephone call. Participants will be asked regarding exacerbations. A sputum sample will be left for collection by the participant

.Participants will count surplus medication and advise the researcher of the tablet count.

### 10.1.5 Follow Up (Week 12 +/- 7 days) Procedures

For those patients who withdraw from the trial / discontinue the study drug prior to 8 weeks or following the completion of 8 weeks of treatment, the CI or designee will contact the patient by telephone 4 weeks post study drug termination to assess if the patient is experiencing any adverse events. Participants will be asked regarding exacerbation status and if applicable exacerbations will be documented.

#### STUDY PROCEDURES AMENDMENT SUMMARY

The study assessments and procedures have been amended in order to observe national Coronavirus lockdown guidelines and to ensure appropriate shielding of the vulnerable participant population. The researcher will conduct the remaining study visits via telephone (including review of online health records) in order to collect data regarding adverse events, safety data, study drug compliance and complete the study questionnaires. It will no longer be possible to measure lung function or collect blood samples.

Table 2	Screening	Visit 1	Visit 2 week 4 (+/-7days)	Visit 3 week 8 (+/-7days)	Follow up week 12
Informed Consent	Х				
Inclusion/Exclusion Criteria	X				
Demographic Data	Х				
Medical History	Х	Х			
Medications	Х	Х	Х	Х	
Vital signs & BMI		Х			
Documentation of exacerbations	X	Х	Х	Х	Х
Randomisation/ Registration		Х			
CAT		Х	Х	Х	
EQ-5D-5L		Х	Х	Х	
Drug administration		Х	Х		
Sputum sample	Х	Х	Х	Х	
Adverse events		Х	Х	Х	Х

## Table 2: Schedule of Assessments EViSCO study

\*In some cases it may not be possible to facilitate lung function testing at the screening visit. In such cases patients who otherwise meet the trial eligibility criteria will be invited to return to have lung function measurement in order to complete the screening procedures. Confirmation of lung function indices must occur prior to trial enrolment.

\*\*At the screening visit a U&E sample will only be sent if there are no previous U&E results from the previous 4 months. A screening U&E sample may be repeated at the discretion of the researcher if there is clinical concern that historic values are borderline.

\*\*\*Bronchoscopy will only be performed in participants that consent to the sub-study. In addition bronchoscopy may not be undertaken on the same day as visit 1 and visit 3 but ideally will be facilitated within the bronchoscopy list.

### **10.2 Study Procedures**

## 10.2.1 Sputum sampling

Sputum will be obtained via spontaneous sputum production. Sputum will be transferred to BHSCT for EBV qPCR in line with current infection control measures. .

## 10.2.2 Research Blood Sampling

Research blood samples will no longer be taken.

### 10.2.3 Bronchoscopy

No further research bronchoscopy will take place.

### 10.2.4 EQ-5D-5L

EQ-5D-5L is a standardised measure of health status developed by the EuroQol Group in order to provide a simple, generic measure of health for clinical and economic appraisal. Applicable to a wide range of health conditions and treatments, it provides a simple descriptive profile and a single index value for health status that can be used in the clinical and economic evaluation of health care as well as in population health surveys. Patients will complete the EQ-5D-5L 3 via telephone.

## 10.2.5 COPD Assessment Test (CAT)

The COPD Assessment Test (CAT) is a patient-completed assessment index that is designed to measure and quantify health related outcomes in patients with chronic airflow limitation. This assessment index is a short (8 point) and simple questionnaire that patients should complete independently. It has been shown to correlate well with symptoms, disease activity and disability. Patients will complete the CAT via telephone.

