### **7.2 Analysis of secondary, exploratory and other safety outcomes**

The lung function outcomes will be reported using Mean (SD) or Median (p25 to p75) in patients with COPD. The change in lung function from baseline to week 8 in the two groups will be analysed using independent t-test or non-parametric alternative. The mean at baseline versus the mean at week 8 within each group will be analysed using a paired t-test or non-parametric alternative.

Exploratory subgroup analyses will be performed on the lung function outcomes for EBV suppression. Analysis of Covariance will be used to assess differences in

treatment effects between the subgroups and will be reported using mean difference and 99% CI.

Tolerability of valaciclovir will be assessed by measuring participant compliance at visit 2 and 3. The compliance (%) will be reported using mean (SD) or Median (p25 to p75) and will be analysed using independent t-test or non-parametric alternative

The change over time in CAT score and EQ-5D will be reported using Mean (SD) or Median (p25 to p75). The change from baseline to 8 weeks will analysed using independent t-test or non-parametric alternative.

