**Table x.x: CAT Questionnaire Descriptive Statistics**

	Valaciclovir			Placebo		
	Baseline	Week 4	Week 8	Baseline	Week 4	Week 8
Cough	xx.x (x.x)	xx.x (x.x)	xx.x (x.x)	xx.x (x.x)	xx.x (x.x)	xx.x (x.x)
Phlegm/ mucus	xx.x (x.x)	xx.x (x.x)	xx.x (x.x)	xx.x (x.x)	xx.x (x.x)	xx.x (x.x)
Chest Tightness	xx.x (x.x)	xx.x (x.x)	xx.x (x.x)	xx.x (x.x)	xx.x (x.x)	xx.x (x.x)
Breathlessness	xx.x (x.x)	xx.x (x.x)	xx.x (x.x)	xx.x (x.x)	xx.x (x.x)	xx.x (x.x)
Limited Activities at Home	xx.x (x.x)	xx.x (x.x)	xx.x (x.x)	xx.x (x.x)	xx.x (x.x)	xx.x (x.x)
Confidence in Leaving Home	xx.x (x.x)	xx.x (x.x)	xx.x (x.x)	xx.x (x.x)	xx.x (x.x)	xx.x (x.x)
Sleeps Soundly	xx.x (x.x)	xx.x (x.x)	xx.x (x.x)	xx.x (x.x)	xx.x (x.x)	xx.x (x.x)
Energy	xx.x (x.x)	xx.x (x.x)	xx.x (x.x)	xx.x (x.x)	xx.x (x.x)	xx.x (x.x)
Total	xx.x (x.x)	xx.x (x.x)	xx.x (x.x)	xx.x (x.x)	xx.x (x.x)	xx.x (x.x)

Table x.x: EQ-5D Descriptive Statistics

EQ: 5D (sub scales)		Valaciclovir			Placebo		
		Baseline	Week 4	Week 8	Baseline	Week 4	Week 8
Numbers reporting some problem – score 2 or above	Mobility	n/N (%)					
	Self-care	n/N (%)					
	Usual activities	n/N (%)					
	Pain/discomfort	n/N (%)					
	Anxiety/Depression	n/N (%)					
EQ: 5D (VAS)		x.x (x.x to x.x)					
Index Score		x.x (x.x to x.x)					

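### CAT and EQ-5D-5L moved to telephone during the trial, and the SAP's change-score t-test allows for neither the baseline score nor mode/period: a small loss of precision in exploratory outcomes

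*Protocol*

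**What the plan says.** Protocol 10.2.5 introduces the CAT as a patient-completed index, a "simple questionnaire that patients should complete independently", and closes with "Patients will complete the CAT via telephone". Section 10.2.4 also moves the EQ-5D-5L to the telephone.

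The visit sections differ from each other. For baseline (10.1.2) the wording is "Participants will complete CAT and EQ-5D-5L assessments", in a visit that also covers vital signs, BMI, blood and sputum, with no mention of a call. For week 4 (10.1.3) it is "CAT and EQ-5D-5L assessments will be completed remotely via telephone call", and for week 8 (10.1.4) "Participants will complete CAT and EQ-5D-5L assessments remotely via telephone call". The amendment summary explains the difference: "The researcher will conduct the remaining study visits via telephone". It lists completion of the questionnaires among the purposes of those calls, next to adverse events and drug compliance.

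Both instruments are clinical exploratory outcomes, assessed from baseline to week 8 (Protocol 5.3.3, SAP 2.3). SAP 7.2 gives the test: "The change from baseline to 8 weeks will analysed using independent t-test or non-parametric alternative". SAP 8.4 reports a mean difference with a 95% interval, and the Appendix 1 table of exploratory outcomes has one pooled row per instrument. SAP section 7 says that t-tests for continuous outcomes may be followed by ANCOVA; it names baseline FEV1 and leaves any further covariate open.

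**The concern.** A change score has a simple meaning when both scores were obtained in the same way. A participant whose baseline was completed at a visit and whose week 8 was taken over the telephone has a change that contains the treatment effect, the effect of switching mode, and whatever lockdown did to the answers. Someone who finished before the amendment has only the first of these. The SAP puts both kinds of participant into one two-sample test.

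Some items could plausibly respond to lockdown itself: the CAT table in SAP Appendix 1 includes "Confidence in Leaving Home", and the amendment summary refers to shielding of participants.

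The SAP was written with the amendment in view. It cites Protocol Version 4.0 of 22/04/2020, repeats the COVID footnotes and adds a COVID-19 sensitivity analysis. But that analysis covers the primary outcome only and excludes confirmed cases, so it does not deal with mode or period. What is at stake is the precision of the arm comparison, and how the reported within-arm change is read, for the trial's patient-reported measures.

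**Working it through.** **1. Which change scores are mixed.** Setting the visit sections side by side, with section 10.1.2 for baseline and section 10.1.4 for week 8:

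| Participant | Baseline | Week 8 |
|---|---|---|
| Finished before the amendment | visit | visit |
| Crossed the amendment | visit | telephone |
| Enrolled after it, if any | visit if section 10.1.2 governs, remote if the last sentence of section 10.2.5 does | telephone |

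The last row shows why 10.1.2, 10.2.4, 10.2.5 and the amendment summary need to be reconciled.

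**2. Inputs.** The documents give no SD for CAT change, no size for a mode or lockdown shift and no share of participants assessed remotely. Assumed: SD of change 6 points, shift d = 2 to 4 points, share p of week-8 scores taken remotely 25% to 50%. Where a number per arm is needed I use 31, the evaluable number in Protocol 13.1. That figure was set for EBV suppression, not for CAT.

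**3. Effect on the standard error.** An unmodelled shift d in a share p adds variance p(1 − p)d² to the change score.

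- p = 0.25, d = 2: 0.1875 × 4 = 0.75; 0.75/36 = 2.1%; √1.021 = 1.010.
- p = 0.50, d = 4: 0.25 × 16 = 4.0; 4.0/36 = 11.1%; √1.111 = 1.054.

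The standard error of the arm difference therefore rises by about 1% to 5%. Only d/SD matters (here 1/3 to 2/3), so the same percentages apply to EQ-5D at the same ratio.

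**4. Effect on the reported within-arm change.** The mean change moves by p × d = 0.25 × 2 = 0.5 to 0.50 × 4 = 2.0 points, by the same amount in both arms in expectation.

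**5. Effect on the arm comparison.** Mode is fixed by the calendar, and allocation is 1:1 and double-blind, so mode is unrelated to arm. Simulating the unadjusted t-test with 31 per arm and half the participants affected (20,000 runs) gave a type I error of 0.048 for a shift of 0.5 SD and 0.049 for 1 SD.

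A one-SD chance imbalance in the remote share moves the difference by d√(2p(1 − p)/31): 2 × √(0.375/31) = 0.22 to 4 × √(0.5/31) = 0.51 points. This is not an additional harm. It equals √(2 × added variance/31), that is √(2 × 0.75/31) = 0.22 and √(2 × 4.0/31) = 0.51, so the t-test's standard error in step 3 already contains it.

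**6. In terms of power.** Take 31 per arm, half affected, and a true difference that would have 80% power without a shift (0.71 SD). Power becomes 79.4% for a shift of 0.25 SD (1.5 points at SD 6), 77.6% for 0.5 SD (3 points) and 70.7% for 1 SD (6 points, outside the range assumed above).

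**7. If few participants crossed.** Protocol 5.5 plans 4 recruits a month and 8 weeks (2 months) of treatment, so about 4 × 2 = 8 are on treatment at any time. If enrolment stopped at the amendment, the share is 8/88 = 9%. Then p(1 − p) = 0.0826, the added variance is 0.33 to 1.32 (0.9% to 3.7%), the standard error rises 0.5% to 1.8%, and the mean change moves 0.2 to 0.4 points.

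**The case against.** The strongest reply is that randomisation already takes care of this. Mode and lockdown are independent of arm, the test keeps its level, and the outcomes are exploratory, with no sample size or decision resting on them. All of that stands. A reader might infer that mixed modes bias the treatment comparison or inflate false positives; the design does not support that, and step 5 shows nominal type I error.

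A reader might also infer that the CAT is invalid by telephone because it has to be completed alone. Section 10.2.5 says that patients should do so, not that they must, and it still has patients completing it. They can choose their own answers on a call. That the researcher asks the questions is a fair reading of the amendment summary, not its wording. What remains is an unexplained departure from the stated manner of completion.

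Nor does the SAP rule out adjustment. Section 7 allows ANCOVA with covariates as needed, and Protocol 13.2 does too. The gap is narrower: the covariates most relevant here, the baseline score and mode/period, are not named, and leaving them open is not pre-specification.

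The documents do not show that shielding moves particular items, or by how much. Item scores are tabulated descriptively only, and the paired within-arm tests in SAP 7.2 are for lung function, so the blurred within-arm change is a matter of description. The telephone share may also be well below 25%: the footnote to the schedule of assessments requires lung function before enrolment, which the amendment summary says can no longer be measured. That enrolment therefore stopped is an inference that the documents do not state.

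**Conclusion.** The point holds as a minor one. Weeks 4 and 8 are by telephone, baseline is described at a visit, and the planned comparison of pooled change scores names neither the instrument's baseline score nor mode or period. The cost is a standard error about 1% to 5% larger than necessary on the assumed inputs (SD 6, shift 2 to 4 points, share 25% to 50%), or about 0.5% to 2% if only some 9% crossed the amendment. The descriptive within-arm changes also mix treatment-period change with mode and lockdown. The documents support no claim of a biased arm comparison or an inflated type I error. The case for acting is that the remedy uses data already collected and costs almost nothing.

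**What to change.** In SAP 7.2 and 8.4, replace the change-score t-test for CAT total, EQ-5D index and EQ-5D VAS with ANCOVA of the week-8 score. The covariates are the same instrument's baseline score and an indicator for whether the week-8 assessment fell before the amendment (visit) or after it (telephone), derived from the visit date. Show the within-arm changes separately by that indicator. State that the indicator captures mode and lockdown together and cannot separate them, since the two coincide.

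In the Protocol, reconcile 10.1.2, 10.2.4, 10.2.5 and the amendment summary, so that it is clear how each assessment, including any baseline after the amendment, was completed.

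The cost is a change of SAP wording and one degree of freedom for the indicator. Adjusting for the baseline score should itself help: with equal variances at the two times and correlation ρ between them, the residual variance is (1 + ρ)/2 of the change-score variance, which never exceeds 1.

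I would not switch to paper forms sent to the home. They would add a third mode to visit and telephone, and a risk of unreturned forms.

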### 10.2.6 Pharmacy (prescribing, randomisation and dispensing)

Prescriptions must not be signed prior to eligibility being confirmed. The date that the prescription form is signed (i.e. requested) cannot be prior to date on which eligibility is confirmed. the date of study drug dispensed by Pharmacy is the randomisation date. The eligibility checklist and stickers cannot be signed off until all results of the tests required to confirm eligibility are completed and available. The study drug start date cannot be before prescription pick up date and must be accurately recorded as this relates to study drug compliance.

